5.5 Supply and Dispensing of Intervention Food at the Study Site

A 12-week supply of individually-wrapped walnut packets will be given to intervention-group participants at enrollment in the study. Those randomized to the control group will receive a 12-week supply of walnuts at the final study visit.

The California Walnut Commission will ship the walnuts to the study site in boxes of 200 individually-wrapped samples in 2 installments – in June 2017 and August 2017. Walnuts will be shipped and kept in cold storage according to the attached protocol. If a participant has concerns about the quality of the walnuts, they will contact the study coordinator who will initiate the following protocol from the California Walnut Commission:

- 1) Have participant return package and remaining product
- 2) Check walnut batch (lot number, date, size of package) where package obtained, if possible
- 3) Contact [name] RD, directly and immediately.

[name] RDN, FAND

[contact]

[contact]

Dosage/Dosage Regimen

We will test a dose of 28g of walnuts daily for the experimental group participants. The walnuts should ideally be consumed without added salt or roasting. This whole-food supplement will be given in conjunction with dietary advice to replace consumption of added sugars and refined carbohydrates

Dispensing

The study coordinator will provide a 12 week supply of walnuts to the intervention participants at the enrollment visit. The study coordinator will provide an equivalent supply of walnuts to the control participants at the study conclusion visit.

Administration Instructions

The participants will consume one 28-gram packet of walnuts daily. This may be consumed at one sitting or throughout the day. Walnuts should replace added sugars or products with refined carbohydrates.

Supply of Food Supplement at the Site

The individually wrapped walnut packages will be delivered from the California Walnut Commission in 2 installments. The first in early June and the second in early August.

Storage

The individually wrapped walnuts will be stored in cold storage until they are given to the participants.

Measures of Treatment Compliance

Subjects will be asked to keep a patient diary noting the day and date they consume their allocated walnut packet and any adverse events. They will be asked to bring their patient diary to each study visit.

We will also test measures of walnuts consumption: whole blood RBC fatty acids composition; serum lipids which include LDL HDL, TC ApoA- 1, Apo B, triglycerides.

Allowed Medications and Treatments

Standard therapy for all medical conditions is allowed except for treatments noted in the exclusion criteria described above.

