5.3 Study Intervention

Participants in the Usual Care group and Walnuts groups will receive usual counseling and care, including general dietary and lifestyle counseling provided to all patients with diagnosed prediabetes, recommending a diet high in vegetables, fruits, whole grains, lean protein and dairy. Those in the Walnuts intervention group will receive initial dietary counseling to describe the high refined carbohydrate foods to be replaced with the

intervention walnut supplement. The intervention group will receive one, individually-wrapped, 28g packet of raw, unsalted walnuts to be consumed daily for a total of 12 weeks to replace specific high refined carbohydrate snacks. Individually packaged walnuts will be donated by the California Walnut Commission, who will not have a role in the design, procedures or interpretation of this study. Participants will be required to log their food exchanges on a daily basis. This study is designed as a non-blinded trial, therefore to protect against greater than usual consumption of walnuts by the Usual Care group during the intervention period, we will offer walnut supplementation at the end of the trial to these participants. Participants in the Usual Care group will be instructed to carry out usual diet and lifestyle changes for the 12-week duration, and will receive walnut supplementation, identical in dose and duration to the intervention group, after the completion of the study.

The following treatment regimens will be used:

- Walnuts “Now”: 28g of individually-wrapped raw, unsalted walnuts consumed daily for 12 weeks during the study period
- Walnuts “Later”: Usual diet during the study period. The participants will be provided with an equivalent amount of individually wrapped walnut packets for their daily use after the study period has concluded.

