5.4 Randomization and Blinding

Randomization: Participants will be randomly assigned to two groups of 20 participants each: “Walnuts Now” Or “Walnuts Later”. We will block our randomization by two important potential confounders: sex (female or male) and age categories (<50 or \geq 50 years). We will generate stratum-specific sequential ID numbers to randomly allocate individuals to intervention groups in blocks of four. Study staff will be blinded to the linkage between ID numbers and group assignment. Upon enrollment, each participant's stratum will be identified and the next sequential ID number from that stratum was assigned. At the end of the baseline visit, the interviewer will open a sealed, opaque envelope pre-printed with the sequential ID number revealing the intervention group assignment to the participant.

Blinding

Due to the objectives of the study, the identity of test and control treatments will be known to investigators, research staff, or patients.

This study is designed as a non-blinded trial, therefore to protect against greater than usual consumption of walnuts by the Usual Care group during the intervention period, we will offer walnut supplementation at the end of the trial to these participants. Participants in the Usual Care group will be instructed to carry out usual diet and lifestyle changes for the 12-week duration, and will receive walnut supplementation, identical in dose and duration to the intervention group, after the completion of the study.

Because of the behavioral nature of the intervention, study staff who administer the intervention and study participants will not be blinded to their intervention group assignment, however we will blind the outcomes assessments – clinical labs and amino acid analyses will be done by labs without knowledge of intervention group.

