5.7 Measures Collected at Each Visit

Table 1: Measurements at each Study Visit				
Visit	Telephone Screening (Week 0)	Baseline visit (Week 1)	Telephone Mid-Point (6 weeks)	Study completion (12 weeks)
Informed Consent	Verbal informed Consent	Written informed consent		
Questionnaires	Initial eligibility screen	Demographic questionnaire Block food frequency Self-efficacy		Acceptability Palatability Adherence Block food frequency Self-efficacy
Clinical measurements		Height Weight Waist circumference Blood pressure Capillary blood glucose		Height Weight Waist circumference Blood pressure
Laboratory analyses		Fasting glucose HbA1c Lipids BCAA, AAA, acylcarnitines		Fasting glucose HbA1c Lipids BCAA, AAA, acylcarnitines
Counseling		Dietary and exercise counseling for both intervention and control arms	Check-in for diet and exercise changes Adherence to walnut supplement for "Walnuts Now" group.	
Dispensing of Study Intervention		"Walnuts Now" Intervention Group receives a 12-week supply of walnuts		"Walnuts Later" Control Group receives a 12-week supply of walnuts

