5.7 Statistical analyses

This trial is designed as a feasibility study and an investigation of the acceptability of the walnut intervention. The second aim is to establish preliminary efficacy for changes in fasting glucose, HbA1c and amino acid levels, for determination of sample size in a future clinical trial. Therefore, we have chosen to enroll a goal of 40 participants, including 20 in the intervention and 20 in the control groups.

Specific Aim 1: Aim 1: Determine a) feasibility for recruitment and retention into a randomized controlled trial of daily walnut supplementation, and b) acceptability and adherence to the intervention containing 28g of walnuts daily, compared with usual care in individuals with prediabetes.

Feasibility and acceptability. We will assess feasibility based on number screened and enrolled in the proposed randomized clinical trial for our goal of 40 participants. Retention over the 12-week intervention period will be assessed by number of participants who complete the final study visit at the conclusion of the intervention period. Palatability will be assessed by a 100mm visual analog scale. We will also assess acceptability of the walnut intervention, and its dose and frequency through a targeted questionnaire at the end of the intervention period. Adherence will be measured through self-report (food diaries) as well as the food frequency questionnaire administered at study completion. All questionnaires will be administered by our research assistant.

Aim 2: Determine preliminary efficacy measures for change in a) fasting glucose, HbA1c and lipid levels, b) dietary quality score and c) BCAA levels in the intervention group to inform a larger future randomized controlled trial.

Fasting glucose, HbA1c and lipids: We will obtain fasting blood samples at enrollment and at the conclusion of the study. One aliquot of serum tube of blood will be sent for fasting glucose, lipids, ApoA1 and B, and HbA1c measurement, and one aliquot of plasma will be sent for metabolomics analyses. Additional aliquots of plasma and serum will be frozen for future research purposes. We will establish preliminary efficacy for each of these measurements.

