Dietary Quality: A Block food frequency questionnaire will be administered to participants at enrollment and completion of the study period. This questionnaire will use patient recall to gather frequency and serving size data for all participants. We will use the responses in this questionnaire to determine consumption of foods grouped based on likeness and culinary usage. These categories will then be transformed into 2 dietary scores: the Healthy Eating Index-2010 score, based on the Dietary Guidelines for Americans, which is a continuous score ranging from 0-100, with a score of 100 representing the optimal diet. We will also calculate the Mediterranean Diet Score, with possible values from 0-55, with 55 representing the diet most congruent with the Mediterranean diet.

BCAA, AAA and acylcarnitines: Targeted amino acid and acylcarnitine levels will be measured at baseline and at 12 weeks, post-intervention using triple quadrupole (MS/MS) and gas chromatography instruments. We will collaborate with the West Coast Metabolomic Center on the metabolomics analyses and interpretation.

Statistical Analysis: This is designed as a parallel group controlled trial, randomized on dichotomized age (<50 or \geq years) and sex (female or male). We will use Fisher's exact test and Student's t-test to compare mean baseline demographic and clinical

characteristics between the intervention and control groups. Using information from the Block food frequency questionnaire, we will construct a continuous dietary quality score using the Healthy Eating Index 2010 and Mediterranean Diet Score criteria. We will use analysis of covariance to compute the adjusted mean for our outcome variables of fasting glucose, HbA1c, HDL, LDL, total cholesterol and amino acid levels. In analysis of covariance, the baseline value of outcome variables will be used as a covariate for the computation of adjusted means between the two groups after intervention.

Expected Results: We believe that walnut supplementation will be acceptable at a dose of 28g daily. We expect to be able to recruit 40 participants within 3 months, and retain >75% for the full 12 weeks of the intervention. We expect to see a trend towards significant change in the BCAA and AAA measurements and some improvements of fasting glucose and HbA1c in the “Walnut” group compared to the “Usual care” group.

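### Aim 1b adherence is analysed from participant report only: no routine count of unused walnut packets is planned, and the red-cell fatty acid measure named in section 5.5 is not carried into the schedule or analysis

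*Combined protocol and SAP*

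**What the plan says.** Adherence to 28 g of walnuts daily is part of Aim 1b (section 2).

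- **Dose and supply.** Section 5.5: "The participants will consume one 28-gram packet of walnuts daily". Section 5.3 sets the regimen: "28g of individually-wrapped raw, unsalted walnuts consumed daily for 12 weeks during the study period". The supply is handed over once: "A 12-week supply of individually-wrapped walnut packets will be given to intervention-group participants at enrollment in the study".
- **Compliance measures, section 5.5.** "Subjects will be asked to keep a patient diary noting the day and date they consume their allocated walnut packet". The same subsection then adds red-cell fatty acid composition and serum lipids, including apolipoproteins, as measures of walnut consumption.
- **Adherence analysis, section 5.7 (Statistical analyses).** "Adherence will be measured through self-report (food diaries) as well as the food frequency questionnaire administered at study completion". The same section describes the questionnaire as based on recall.
- **Other adherence information.** Section 5.3 requires a daily log of food exchanges. Table 1 has an adherence check for the Walnuts Now group at the 6-week call and an adherence questionnaire at completion.
- **Return of product.** The only return described is in section 5.5, for packages with a quality concern.

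**The concern.** The dose comes in a unit that can be counted, one wrapped packet per day, and every packet is issued at baseline. Yet each source that feeds the adherence result is something the participant says or writes. Diaries are to be brought to study visits, but the only in-person visit after dispensing is the one at completion. A diary filled in late could look the same as one kept daily.

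Participants know their assignment (section 5.4), and section 5.9 describes them as motivated volunteers, so over-reporting is plausible. If intake is overstated, the pilot will give too favourable a picture of whether a daily packet is achievable. The Aim 2 estimates, which are meant to inform the size of a later trial, would also carry dilution from non-adherence that nobody can see. Section 2.3 further hopes to learn whether amino acids can serve as adherence markers beyond self-report. That question needs a reference measure that is not itself self-report.

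**Working it through.** The documents print no packet count, adherence target or power calculation, so there is no stated figure to reproduce.

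**1. Packets.** 12 weeks × 7 days × 1 packet = 84 per participant. Section 5.4 states: "Participants will be randomly assigned to two groups of 20 participants each". The intervention arm therefore receives 20 × 84 = 1,680 packets. A count measures one person's use in steps of 1/84 = 1.2 percentage points.

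**2. What the named biological measures supply.**

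| Measure | Named in 5.5 | Lab procedures (5.6) | Table 1 | Analysis (5.7) |
|---|---|---|---|---|
| Red-cell fatty acids | yes | no | no | no |
| Serum lipids | yes | yes | yes | yes, as Aim 2 outcomes |

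Section 5.6 describes serum and plasma aliquots only; no red-cell or whole-blood aliquot is mentioned. Lipids cannot cleanly serve as both adherence measure and outcome: unchanged lipids could mean that the walnuts were not eaten or that they had no effect. Neither measure gives the fraction of packets taken.

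**3. Size of a possible gap (assumed; the documents give no rate).** Gap in packets = over-report × 84:

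- 5 points: 0.05 × 84 = 4.2
- 10 points: 0.10 × 84 = 8.4
- 20 points: 0.20 × 84 = 16.8

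**4. Set against sampling error.** The 95% half-width for mean adherence is t(0.975, n−1) × SD / √n. The between-person SD is assumed to be 10, 20 or 30 points.

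- n = 20: 4.7, 9.4 or 14.0 points
- n = 15 (0.75 × 20, the floor of the retention expectation "retain >75% for the full 12 weeks of the intervention"): 5.5, 11.1 or 16.6 points

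An over-report of 10 to 20 points is thus of the same order as the sampling error or larger, and the confidence interval would not reveal it.

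**5. What a count can and cannot show.** Suppose true use is 60% (50.4 packets) and the diary says 80% (67.2).

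- All 84 − 50.4 = 33.6 unused packets come back: the count reads 50.4 and the 16.8-packet gap is visible.
- Half of the unused packets (16.8) are thrown away unreported: the count reads 84 − 16.8 = 67.2, and the gap disappears.
- Nothing is brought back: the count reads 84/84 = 100%.

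The count is therefore an upper bound, and it needs a rule for packets that are not brought back.

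**6. Denominator.** If it is days to the completion visit, full use of the supply with a visit at day 91 (illustrative) scores 84/91 = 92%. With min(days, packets dispensed) it scores 84/84 = 100%. A visit at day 77 with 77 packets used also scores 77/77 = 100%.

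**The case against.** The strongest reply is that the plan already looks beyond self-report. The subsection that introduces the diary goes on to red-cell fatty acids and lipids, and section 2.3 raises amino acids. Fatty acids reflect intake, which a packet count does not. The plan also has a food-exchange log, a mid-study call and a completion questionnaire. A count fails in the same direction as the diary, because someone who over-reports can also discard packets. On this view the real gap is the unscheduled fatty acid measure, and a count is an optional extra in a 40-person pilot.

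Much of this stands. A reader might infer that the protocol names no measure except self-report; section 5.5 contradicts that. The accurate statement is that the Aim 1b analysis uses self-report only and that the fatty acid measure is not carried through. Nor can one say that packets are never returned, since quality complaints trigger a return. The 6-week call weakens the picture of an entirely unobserved diary, although it too yields participant report.

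The objection does not remove the need for a count. As the plan stands, the fatty acids have no scheduled sample or analysis, and they would not give the proportion of packets used even if they had. A one-sided bound is still informative: a diary total above the number of packets not returned cannot be right.

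**Conclusion.** The point holds as a cheap improvement to one of the pilot's first-aim outcomes. Adherence is analysed from participant report, 84 countable packets per person are issued with no routine count planned, and the one named measure of consumption that is not also an efficacy outcome is missing from the laboratory procedures, Table 1 and the analysis.

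The figures 84 and 1,680 follow from the documents. The 4.2 to 16.8 packets rest on an assumed over-report of 5 to 20 points, and the interval widths on an assumed SD; the documents support neither that over-reporting will occur nor its amount.

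A reader might also infer that the adherence result decides whether 28 g goes into the larger trial. The documents give no adherence threshold or progression rule; the stated use of the pilot is efficacy estimates to inform sample size. Nor would a count be an objective measure of walnuts eaten: it shows packets not returned.

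**What to change.** 1. **Section 5.5 and Table 1.** Ask Walnuts Now participants to bring all unopened packets to the completion visit. Record packets dispensed, returned, and reported as discarded or returned for quality reasons, and whether the participant confirms that all leftovers were brought.
2. **Section 5.7 (Statistical analyses).** Report (dispensed − returned − discarded) / min(days from baseline to completion visit, packets dispensed), capped at 100%, beside the diary figure and with the difference between them.
3. **Missing counts.** Treat the count as missing, not as 100%, when the participant does not attend or does not confirm that all leftovers were brought. Report how many participants have a count.
4. **Interpretation.** Describe the count as an upper bound on intake, because sharing and unreported discarding are not detected and discards are themselves self-reported.
5. **Fatty acids.** Reconcile section 5.5 with section 5.6, Table 1 and the analysis section: either add the red-cell sample, assay and analysis, or remove the measure.

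For the count, the cost is that participants carry packets back and the form gains a line at a visit already planned. Scheduling the fatty acid assay would cost more; the documents give no figure.

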Eligible participants will be randomized into “Walnuts Now” and “Walnuts Later” groups. They will complete questionnaires about demographic and medical history, health-related behaviors including satiety, and medications. A research coordinator will measure height, weight, waist circumference and blood pressure. The participants will undergo venipuncture and fasting blood draw. One tube of serum will be sent to Quest for measurement of fasting glucose, hemoglobin A1c and serum lipids as well as apolipoprotein A2 and B. One tube will be aliquotted into 1mL cryogenic tubes. One aliquot of plasma will be shipped to the West Coast Metabolomics Center at the University of California, Davis for amino acid and acylcarnitine analyses. The remaining serum and plasma aliquots will be de-identified, frozen at -80C and stored for future analyses.

All participants will receive handouts regarding a healthy diet to prevent diabetes.

The research coordinator will dispense 12-week supply of individually-wrapped, raw walnuts to “Walnuts Now” group.

6-week Telephone Follow-up

The research coordinator will reach out to study participants by phone at 6 weeks to remind intervention participants of daily walnut intervention, give a reminder of healthy eating habits to all participants, and schedule Study Conclusion visit.

Study Completion Visit

At study completion, all participants will be invited back for a study completion visit. At this visit, a research assistant will record height, weight, blood pressure and waist circumference. The participants will undergo venipuncture and fasting blood draw. One tube of serum will be sent to Quest for measurement of fasting glucose, hemoglobin A1c and serum lipids as well as apolipoprotein A2 and B. One tube will be aliquotted into 1mL cryogenic tubes. One aliquot of plasma will be shipped to the West Coast Metabolomics Center at the University of California, Davis for amino acid and acylcarnitine analyses. The remaining serum and plasma aliquots will be de-identified, frozen at -80C and stored for future analyses.

All participants will receive handouts regarding a healthy diet to prevent diabetes.

The research coordinator will dispense 12-week supply of individually-wrapped, raw walnuts to “Walnuts Later” group.

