Grade 4 Life-Threatening	Extreme limitation in activity, significant assistance required significant medical intervention/therapy required, hospitalization or hospice care probable.

3. AE Attribution Scale –AEs will be categorized according to the likelihood that they are related to the study intervention. Specifically, they will be labeled either definitely, probably, possibly or unrelated to the study intervention.

4. Expected Risks – There is minimal risk with participating in the walnut intervention. Expected risks to the subject are mild gastrointestinal symptoms due to inclusion of walnuts in a normal daily diet. These risks are considered to be minimal and are addressed in the protocol and consent form. Participants will have a contact number to report any potential adverse events that occur in between scheduled study visits. They will also have an opportunity to privately discuss any other physical complaints due to inclusion of walnuts.

5. SAE Reporting - SAEs that are unanticipated, serious (grades 3 and 4), and/or possibly related to the study intervention will be reported to the Independent Monitor, IRB, CTSA at UCSF, and NIH in accordance with requirements. Anticipated SAEs or those unrelated to the study intervention will be reported to the same individuals/entities in accordance with requirements.

If abnormal lab values are discovered during the study, the PI will be notified and will address this issue as early as possible. If fasting glucose is found to be abnormally low (greater than or equal to 40 mg/dL and below 70 mg/dL), the participant will receive a call from the study coordinator asking if they are experiencing adverse effects such as nausea or lightheadness. This mild hypoglycemia will be treated with sugar intake. A severely low blood sugar (<40 mg/dL) will be flagged as a critically low value by the study coordinator who will notify the principal investigator immediately or within half an hour of receiving the notification. The participant will be called to proceed to the emergency room and will be withdrawn from the study. Abnormal lab values will be reported as adverse events only when the Principal investigator deems them to be clinically significant.

6.5.c. Data Quality and Safety Review Plan and Monitoring

1. Data Quality and Management

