a. Description of Plan for Data Quality and Management – The PI will review all data collection forms on an ongoing basis for data completeness and accuracy as well as protocol compliance. A statement reflecting the results of the review will be sent to the NIH in the annual report.

Data quality will be assessed using measures such as time from study visit to data entry, time to resolution of data queries, number of missing forms, and proportion of all study variables queried. Guidelines for concern regarding these measures are outlined below:

Measure	Goal Value	Acceptable Value
time from visit to data entry	< 1 week	< 2 weeks
time to resolution of queries	<2 week	< 2 weeks
number of missing forms	0	< 5%
proportion of variables queried	5%	<10%

b. Frequency of Review –The frequency of data review depends according to the type of data and is summarized in the following table.

Data type	Frequency of review	Reviewer
Subject accrual (adherence to eligibility criteria, randomization)	Monthly	Principal Investigator
Adverse event rates (injuries)	Monthly	Principal Investigator
Out of range laboratory data	Weekly (PI)	Principal Investigator

2. Subject Accrual and Compliance

a. Measurement and reporting of subject accrual, adherence to inclusion/exclusion criteria –Review of the rate of subject accrual, adherence to inclusion/exclusion criteria will occur monthly during the 3 month recruitment phase.

6.5.d Safety Review Plan

Study progress and safety will be reviewed monthly by the PI. A study completion report will be compiled and will include a list and summarization of adverse events. In addition, the annual report will address (1) whether adverse event rates are consistent with pre-study assumptions; (2) reason for dropouts from the study; (3) whether all participants met entry criteria. The report will be signed by the Independent Monitor and will be forwarded to the appropriate IRB and NIH, the UCSF CTSA on an annual basis.

REFERENCES CITED

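### Symptoms are recorded in a walnut-packet diary and no common adverse-event question is put to both arms, so a by-arm reading of adverse events is open to ascertainment bias

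*Combined protocol and SAP*

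**What the plan says.** **The diary.** Section 5.5, under Measures of Treatment Compliance, states: "Subjects will be asked to keep a patient diary noting the day and date they consume their allocated walnut packet and any adverse events". It continues: "They will be asked to bring their patient diary to each study visit". No arm is named.

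**When controls have packets.** The same section states: "Those randomized to the control group will receive a 12-week supply of walnuts at the final study visit". Controls therefore have no packet to log during the 12-week comparison.

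**Scheduled contacts.** At the 6-week call (section 5.6) the coordinator is to "remind intervention participants of daily walnut intervention, give a reminder of healthy eating habits to all participants" and to book the final visit. Table 1 adds a diet and exercise check-in, plus a walnut-adherence check for the Walnuts Now group only. The completion visit consists of body measurements, blood pressure, a fasting blood draw, handouts and dispensing to controls; Table 1 adds questionnaires on acceptability, palatability, adherence, diet and self-efficacy. None of these entries is an adverse-event question, and Table 1 has no adverse-event row.

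**Other routes.** Section 6.5.b, item 4, says: "Participants will have a contact number to report any potential adverse events that occur in between scheduled study visits". It then adds: "They will also have an opportunity to privately discuss any other physical complaints due to inclusion of walnuts". Section 6.5.b also covers abnormal laboratory values, and section 6.2.b promises ongoing safety surveillance in general terms.

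**Use of the data.** Section 6.5.d provides for monthly review by the principal investigator, a completion report that lists and summarises adverse events, and an annual report that addresses "whether adverse event rates are consistent with pre-study assumptions".

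**The concern.** The protocol's definition of an adverse event (section 6.5.b, item 1) covers any subject in the study, so control events count. Yet the one written prompt to record symptoms is attached to an act that only the walnut arm performs during the 12 weeks. Participants and intervention staff know the allocation; the blinded assessment in section 5.4 covers only the clinical laboratory and amino acid analyses.

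The expected events are mild gastrointestinal symptoms. These plausibly also occur without walnuts, and they are easily left unreported unless someone asks. If one arm is prompted and the other is not, a summary shown by arm can suggest that walnuts cause symptoms when the true rates are equal, or exaggerate a real difference. What is at stake is the descriptive tolerability picture that a pilot hands to the larger trial: without comparable control data, a walnut-arm symptom rate cannot be separated from background.

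**Working it through.** **Step 1: each capture route, by arm, during the 12 weeks**

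| Route | Walnuts Now | Walnuts Later | Does it ask about symptoms? |
|---|---|---|---|
| Diary (5.5) | Yes; entries follow the packets | Not stated; no packets to log | Yes, for whoever keeps it |
| 6-week call (5.6, Table 1) | Yes | Yes | None listed |
| Completion visit (5.6, Table 1) | Yes | Yes | None listed |
| Contact number (6.5.b) | Yes | Yes | No; the participant must call |
| Private discussion (6.5.b) | Yes | Worded around walnut intake | Only complaints due to walnuts; no contact specified |
| Laboratory review (6.5.b) | Yes | Yes | No; cannot detect mild gastrointestinal symptoms |
| Safety surveillance (6.2.b) | Yes | Yes | Method not specified |

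The diary is the only row with a written, repeated prompt, and its application to controls is left open. Two readings are possible.

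- *Walnut arm only.* Controls have no prompted recording during the comparison.
- *Both arms.* Controls have a diary whose daily entry does not apply to them, so the adverse-event item loses its cue.

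A third possibility, that controls start a diary when they get their packets, does not help: Table 1 shows no visit after completion at which it could be returned. On any of these readings, capture is likely to be more complete in the walnut arm.

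**Step 2: illustration of size**

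The documents give no adverse-event rate, no capture rate and no numerical pre-study assumption, so there is no figure to reproduce. Everything below except the 20 per arm (section 5.4) is assumed.

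Formulas: observed risk = true risk × capture; expected count = 20 × observed risk; observed risk ratio = walnut capture ÷ control capture when true risks are equal.

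Take a true risk of 20% in both arms and walnut capture of 0.9. The walnut arm then shows 0.20 × 0.9 = 0.18, or 20 × 0.18 = 3.6 participants.

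| Control capture | Control observed risk | Control expected count | Spurious difference | Spurious risk ratio | Chance of Fisher p < 0.05 |
|---|---|---|---|---|---|
| 0.9 | 0.18 | 3.6 | 0 points | 1.00 | 2.2% |
| 0.7 | 0.14 | 2.8 | 4 points | 1.29 | 2.8% |
| 0.5 | 0.10 | 2.0 | 8 points | 1.80 | 5.2% |
| 0.3 | 0.06 | 1.2 | 12 points | 3.00 | 10.4% |

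The last column is an exact binomial enumeration with a two-sided Fisher test at an assumed 0.05; the protocol plans no such test. Over the same unequal captures (0.7 to 0.3), the spurious difference is 2 to 6 points at a true risk of 10% and 8 to 24 points at 40%. The risk ratios do not change with the true risk.

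At a 20% true risk the distortion is between 0.8 and 2.4 participants (3.6 − 2.8 and 3.6 − 1.2). It would seldom reach significance; its effect is on how a descriptive table reads.

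**The case against.** The strongest reply is that no planned analysis depends on this. Section 6.5.d plans a list and summary of events and a check against pre-study assumptions, not against controls. Section 5.7 (Statistical analyses) has no adverse-event endpoint. The trial is a 40-person pilot of a food that the protocol rates as minimal risk. All of this stands, and it limits the severity.

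A reader might also draw stronger conclusions that the documents do not support:

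- *That controls have only a telephone number.* The number is for all participants, and controls also have the 6-week call, the completion visit, laboratory review and the general surveillance commitment. What is true is that none of these specifies a symptom question.
- *That controls have no diary.* The text says subjects, without naming an arm, and a control could record adverse events and bring the diary to the completion visit. A walnut-only diary is the natural reading of the packet wording and the compliance heading, but it is an inference.
- *That adverse-event rates cannot be compared at all.* They could be; the comparison would carry a bias whose size the documents do not let us estimate.
- *That adverse events feed directly into Aim 1 acceptability.* Section 5.7 measures palatability by visual analog scale, acceptability by a targeted questionnaire, adherence by diaries and the food frequency questionnaire, and retention by final-visit completion. Adverse-event counts enter none of these.
- *That a false walnut excess is certain.* The illustration rests wholly on assumed capture rates.

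The objection does not remove the gap itself: the protocol leaves open who keeps the diary and gives no common enquiry for the two arms.

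**Conclusion.** The point holds as a minor weakness in ascertainment. The only named symptom-recording instrument follows walnut packets that controls lack for the 12 weeks, its use by controls is not stated, and no scheduled contact asks either arm about adverse events. In an unblinded trial this makes fuller capture in the walnut arm likely, so any by-arm reading of the adverse-event summary is open to bias of unknown size.

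No planned test is invalidated, because none is planned. The spurious risk ratios of 1.29 to 3.00 show how the mechanism works under assumed captures of 0.9 against 0.7 to 0.3; they are not estimates for this trial. The conclusion about direction assumes that a packet-linked prompt yields more reports than unprompted reporting, and that study staff do not already ask both arms about symptoms in a way the protocol leaves unwritten.

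**What to change.** - Put the same short structured adverse-event question, including gastrointestinal symptoms, to both arms at the existing 6-week call and completion visit, with the same wording and recall period in each arm.
- Add an adverse-event row to Table 1 at those two contacts.
- State in section 5.5 which arms keep the diary and, if controls do, what they are to record.
- In section 6.5.d, base any by-arm adverse-event summary on the common question, and report events found only in the diary separately.

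The cost is one short form and a few minutes at two contacts that all participants already have; no visit is added. The downside is that more minor events will be recorded. Participants will still know their allocation, so some difference in reporting can remain, but the difference created by the method of asking would be removed.
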